9.2 Study completion and post-study treatment

Study completion is defined as when the last subject finishes their Study Completion visit, and any repeat assessments associated with this visit have been documented and followed-up appropriately by the Investigator, or in the event of an early study termination decision, the date of that decision.

All randomized and/or treated subjects will be followed up for an additional 20 weeks period. During the 20 week follow up period, safety monitoring will continue as described in the assessments table, [Table 8-1](#).

All randomized and/or treated subjects who do not continue study visits after receiving treatment should have a safety follow-up call conducted a minimum of CCI after last administration of study treatment. The information collected is kept as source documentation. All SAEs reported during this time period must be reported as described in [Section 10.1.3](#) and the Site Operations Manual. Documentation of attempts to contact the subject should be recorded in the source documentation.

10 Safety monitoring and reporting

10.1 Definition of adverse events and reporting requirements

10.1.1 Adverse events

An adverse event (AE) is any untoward medical occurrence (e.g., any unfavorable and unintended sign [including abnormal laboratory findings], symptom or disease) in a subject or clinical investigation subject after providing written informed consent for participation in the study. Therefore, an AE may or may not be temporally or causally associated with the use of a medicinal (investigational) product.

The investigator has the responsibility for managing the safety of individual subject and identifying adverse events.

Novartis qualified medical personnel will be readily available to advise on trial related medical questions or problems.

The occurrence of adverse events must be sought by non-directive questioning of the subject at each visit during the study. Adverse events also may be detected when they are volunteered by the subject during or between visits or through physical examination findings, laboratory test findings, or other assessments.

Adverse events must be recorded in the Adverse Events CRF under the signs, symptoms or diagnosis associated with them. Severe hypoglycemia is an event requiring assistance of another person to actively administer carbohydrates, glucagon, or take other corrective actions. Definitions of hypoglycemia are provided in [Section 8.3.1](#) and [Table 8-3](#). All other adverse events reported in the CRF should be accompanied by the following information (as far as possible) (if the event is serious refer to [Section 10.1.2](#)):

1. The severity grade
 - mild: usually transient in nature and generally not interfering with normal activities.
 - moderate: sufficiently discomforting to interfere with normal activities.
 - severe: prevents normal activities.
2. its relationship to the study treatment. If the event is due to lack of efficacy or progression of underlying illness (*i.e.* progression of the study indication) the assessment of causality will usually be 'Not suspected'. The rationale for this guidance is that the symptoms of a lack of efficacy or progression of underlying illness are not caused by the trial drug, they happen in spite of its administration and/or both lack of efficacy and progression of underlying disease can only be evaluated meaningfully by an analysis of cohorts, not on a single subject.
3. its duration (start and end dates) or if the event is ongoing, an outcome of not recovered/not resolved must be reported.
4. whether it constitutes a SAE (see [Section 10.1.2](#) for definition of SAE) and which seriousness criteria have been met.
5. action taken regarding with study treatment.
 - All adverse events must be treated appropriately. Treatment may include one or more of the following:
 - Dose not changed
 - Drug interrupted/withdrawn
6. its outcome,
 - a. not recovered/not resolved;
 - b. recovered/resolved;
 - c. recovering/resolving,
 - d. recovered/resolved with sequelae;
 - e. fatal; or unknown.

Conditions that were already present at the time of informed consent should be recorded in medical history of the subject.

Adverse events (including lab abnormalities that constitute AEs) should be described using a diagnosis whenever possible, rather than individual underlying signs and symptoms.

Adverse event monitoring should be continued until end of study visit.

Information about adverse drug reactions for the investigational drug can be found in the IB.

Abnormal laboratory values or test results constitute adverse events only if they fulfill at least one of the following criteria:

- they induce clinical signs or symptoms
- they are considered clinically significant
- they require therapy

Follow the instructions found in the Site Operations Manual for data capture methodology regarding AE collection for subjects that fail screening.

10.1.2 Serious adverse events

An SAE is defined as any adverse event [appearance of (or worsening of any pre-existing)] undesirable sign(s), symptom(s) or medical conditions(s)) which meets any one of the following criteria:

- fatal
- life-threatening

Life-threatening in the context of a SAE refers to a reaction in which the subject was at risk of death at the time of the reaction; it does not refer to a reaction that hypothetically might have caused death if it were more severe (please refer to the ICH-E2D Guidelines).

- results in persistent or significant disability/incapacity
- constitutes a congenital anomaly/birth defect
- requires inpatient hospitalization or prolongation of existing hospitalization, unless hospitalization is for:
 - routine treatment or monitoring of the studied indication, not associated with any deterioration in condition
 - elective or pre-planned treatment for a pre-existing condition that is unrelated to the indication under study and has not worsened since signing the informed consent
 - social reasons and respite care in the absence of any deterioration in the subject's general condition
 - treatment on an emergency outpatient basis for an event not fulfilling any of the definitions of a SAE given above and not resulting in hospital admission
- is medically significant, *e.g.* defined as an event that jeopardizes the subject or may require medical or surgical intervention to prevent one of the outcomes listed above
- Hypoglycemia which requires the assistance of another person to treat must be reported as an SAE.

Medical and scientific judgment should be exercised in deciding whether other situations should be considered serious reactions, such as important medical events that might not be immediately life threatening or result in death or hospitalization but might jeopardize the subject or might require intervention to prevent one of the other outcomes listed above. Such events should be

considered as “medically significant”. Examples of such events are intensive treatment in an emergency room or at home for allergic bronchospasm, blood dyscrasias or convulsions that do not result in hospitalization or development of dependency or abuse.

All malignant neoplasms will be assessed as serious under “medically significant” if other seriousness criteria are not met.

Any suspected transmission via a medicinal product of an infectious agent is also considered a serious adverse reaction.

All reports of intentional misuse and abuse of the product are also considered serious adverse event irrespective if a clinical event has occurred.

10.1.3 Serious Adverse Event (SAE) reporting

To ensure subject safety, every SAE, regardless of causality, occurring after the subject has provided informed consent and until last study visit must be reported to Novartis safety within 24 hours of learning of its occurrence. Detailed instructions regarding the submission process and requirements are to be found in the investigator folder provided to each site.

SAEs occurring after the subject has provided informed consent until the time the subject is deemed a Screen Failure must be reported to Novartis.

Randomized subject's SAEs will be collected between time subject signs ICF until subject has discontinued or stopped study participation, or until CCI after last treatment.

All follow-up information for the SAE including information on complications, progression of the initial SAE and recurrent episodes must be reported as follow-up to the original episode immediately, without undue delay, and under no circumstances later than within 24 hours of the investigator receiving the follow-up information. An SAE occurring at a different time interval or otherwise considered completely unrelated to a previously reported one must be reported separately as a new event.

If the SAE is not previously documented in the IB or Package Insert (new occurrence) and is thought to be related to the study treatment, a CMO & PS Department associate may urgently require further information from the investigator for health authority reporting. Novartis may need to issue an Investigator Notification (IN) to inform all investigators involved in any study with the same study treatment that this SAE has been reported. Suspected Unexpected Serious Adverse Reactions (SUSARs) will be collected and reported to the competent authorities and relevant ethics committees in accordance with EU Guidance 2011/C 172/01 or as per national regulatory requirements in participating countries.

Adverse events and serious adverse events (AE and SAE) will continue to be collected after the CCI post dosing interval, but will generally not be attributed to CFZ533 as pharmacodynamics effects of the drug are anticipated to be back to baseline. These events may help elucidate potential benefits of preserved pancreatic beta-cell function.

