4.1 Rationale for study design

The study employs staggered inclusion of subject cohorts by age and body weight in order to facilitate enrollment of younger subjects in a gradual manner based on emerging safety and tolerability in previous cohorts.

Cohorts are designed according to a descending age range (for the lower age limit). Lower age cut-offs per cohort are selected based on International Council for Harmonization of Technical Requirements for Pharmaceuticals for Human Use (ICH) Topic E11 2001 approximate stages of development: Age 15-21 years late adolescent to young adult; and age 12 to <18 years adolescent. Body weight thresholds are based on anticipated weight boundaries for age ([CDC 2001](#)), noting that permitted weight ranges may impact age of each cohort.

The first cohort will be used to evaluate safety as lower age and weight subjects are exposed in the second cohort. CCI of exposure per age and body-weight cohort will be required before a decision to open the next cohort can be made. CCI considered long enough to observe any potential acute/immediate effects (infusion site reactions, allergic reactions, delayed type hypersensitivity reactions, etc.) and mid-term effects. Effects which may occur at a later point will be monitored throughout the study at any point in time and for all cohorts.

Dosing by body weight categories for the subcutaneous doses (lower body weight receive a lower fixed dose) is justified to provide similar exposures throughout the body weight range (see [Section 4.2](#)).

Commercially Confidential Information

Age: Age range of 12 to 21 years. Cohorts advance from Cohort 1 of young adult to late adolescents (ages ≥ 15 to ≤ 21 years) to Cohort 2, comprised of young adult through adolescents (ages ≥ 12 to ≤ 21 years). The age range enables enrollment of young adult and adolescent subjects in whom new onset T1DM frequently occurs.

The upper age limit of 21 years is selected because the severity of T1DM at diagnosis and T1DM progression in new onset T1DM up to this age are reported to be similar to that of adolescents ([Hao et al 2016](#)).

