There is always a risk of infection with new pathogens that have not been previously encountered and for pathogens against which there are no available or commonly used vaccines

in the first world countries where this study will be conducted. Such examples include cholera and typhoid fever for which vaccines are not standard in these countries. Subjects enrolled in the study must be advised against traveling to areas with endemic diseases that they are not vaccinated against, particularly because preventive travel vaccines will not work during exposure to CFZ533. Immunization with live attenuated vaccines is prohibited for eight weeks prior to first dose administration of study drug ([Rubin et al 2014](#)) until CCI following the last dose.

Commercially Confidential Information

Potential risk of thrombotic events

The risk of thrombotic events with CFZ533 is considered minimal.

Commercially Confidential Information

Comercially Confidential Information

renders an association between CFZ533 and the thrombotic events highly unlikely ([Andrassy et al 2004](#)). Finally, thrombosis rates for CFZ533 should be considered versus the rate seen with standard of care in renal transplant trials.

Overall, while anti-CD154 antibodies are clearly associated with a high risk for thrombophilia, both preclinical and clinical data from an extensive Phase 2 clinical program across healthy subjects and patients across different indications have not indicated an associated risk with CFZ533.

Lymphoproliferative risk

A hypothetical risk for lymphoproliferative disorders for some subjects under strong immunosuppression cannot be excluded for CFZ533. Comercially Confidential Information

Additional safety considerations for CFZ533 in a pediatric population

Immune system maturation in pediatrics: The immune system, adaptive and innate, is deemed functionally competent at 6 years of age, and comparable to that of adults. Thus, this study enrolls pediatric subjects anticipated to have a mature immune system.

CD40 and bone growth: There is no indication of an effect of the CD40-CD154 pathway on linear bone growth. Comercially Confidential Information

CD40 and puberty: There is no known role or involvement of the CD40 pathway in puberty.

In general, the risk in this trial will be managed and minimized by appropriate eligibility criteria, specific dose selection criteria and stopping rules.

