9.1.4 Study stopping rules

The Sponsor, the DMC and Lead Investigator will continually review and *ad hoc* as needed, adverse events and laboratory findings throughout the study, including the number and/or severity of adverse events, cumulative cases of clinically significant adverse events, severe adverse events, clinically significant laboratory changes, except those that are reasonably suspected to be due to extraneous causes.

As a result of the safety review, study recruitment or the study (a part/ or cohort of the study) may be placed on hold pending further safety analysis if Novartis, the DMC, and Lead Investigator, considers that the cumulative number and/or severity of AEs or other clinically significant changes are deemed unsafe to continue recruitment or dosing. Novartis and the Lead Investigator must jointly evaluate the relationship between an adverse event and CFZ533, and decide whether to resume enrollment, or to stop one cohort, all dosing, or to terminate the study prematurely.

Study recruitment will be stopped, pending a full safety review, if any of the following criteria are met:

- At least 2 of the 6 (for Cohort 1) or 3 of the 10 (for Cohort 2) subjects in the same cohort experience a CFZ533-related AE (CTCAE grade 3 or higher) in the first month of treatment.
- Three (3) or more subjects with recurrent and severe systemic infections (CTCAE grade 3) per cohort in the first month of treatment, or more than 50% of all treated subjects at any point in time.
- One (1) or more subjects with a severe allergic reaction (CTCAE grade 3 or higher) to study drug in the first five (5) treated subjects or an incidence of > 20 % thereafter.
- One (1) or more subjects with cytokine release syndrome.
- The sponsor unilaterally requests it.
- The DMC recommends it.

If one of the above stopping rules is met, the Competent Authorities and Institutional Review Board/Independent Ethics Committee (IRB/IEC) will be informed of the temporary halt of study via a Substantial Amendment in accord with local regulations. The study may resume following the safety review, if the Sponsor and DMC, and Lead Investigator agree it is safe to proceed and after approval to restart the study is obtained from the Competent Authorities and IRB/IECs.

Cohort stopping rules are described in the above study stopping criteria list.

Individual stopping rules are listed in the [Section 9.1.1](#).

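### Protocol 10.1.3 sets a time-based default against attributing late AEs and SAEs to CFZ533, which may bias causality coding of late harms and so may reduce SUSAR identification

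*Protocol*

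**What the plan says.** Protocol 10.1.3 says that AEs and SAEs continue to be collected after a post-dosing interval whose length is redacted, "but will generally not be attributed to CFZ533 as pharmacodynamics effects of the drug are anticipated to be back to baseline". It adds that these events may help to show the benefit of preserved beta-cell function.

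Other statements bear on this:

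- **Reporting to the sponsor (10.1.3).** "every SAE, regardless of causality, occurring after the subject has provided informed consent and until last study visit must be reported to Novartis safety". The deadline is 24 hours from awareness.
- **Follow-up for health authorities (10.1.3).** The possible urgent request for more information concerns an SAE that is not previously documented "and is thought to be related to the study treatment".
- **SUSARs (10.1.3).** "Suspected Unexpected Serious Adverse Reactions (SUSARs) will be collected and reported to the competent authorities and relevant ethics committees". No time limit is given.
- **Causality per event (10.1.1).** Each AE on the CRF, other than hypoglycemia, which has its own rules, should carry "its relationship to the study treatment" as far as possible. No cut-off after the last dose is given.
- **Safety review (9.1.4).** "Novartis and the Lead Investigator must jointly evaluate the relationship between an adverse event and CFZ533".
- **Late effects (4.1).** "Effects which may occur at a later point will be monitored throughout the study".
- **Open risk (4.5).** "A hypothetical risk for lymphoproliferative disorders for some subjects under strong immunosuppression cannot be excluded for CFZ533". The same section says that pediatric safety information is not yet available and that unknown risks are possible. The protocol summary states that this is the first pediatric study of CFZ533.

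**The concern.** Whether a serious event becomes a SUSAR depends on two judgements: is it unexpected, and is a causal relationship suspected? The clause in 10.1.3 leans on the second through the calendar alone. It also stands in the section that investigators consult when they report an SAE, directly after the SUSAR paragraph.

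The reason given is that pharmacodynamic effects should have returned to baseline. That is an expectation, in an age group not studied before. Even if it is right, it does not exclude harm that began during exposure and was recognized later. Section 10.2.1 expects subjects on drug not to mount humoral responses to new antigens and warns that serology may be less informative, so an infection acquired on treatment could come to light after washout. The lymphoproliferative risk in 4.5 is another example of a harm that could appear late.

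The paragraph is also lopsided. Late events may inform on benefit but are presumed to say little about harm.

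**Working it through.** The plan states no figure to reproduce on this point. The check has two parts: a comparison of the texts, and the length of the window affected.

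**Texts side by side**

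1. 10.1.1 asks for a relationship to treatment event by event. 10.1.3 gives the expected answer for all events after a certain time. The two can be applied together, because 10.1.3 says only 'generally', but they pull in different directions.
2. 10.1.1 has a default of its own: events due to lack of efficacy or disease progression will usually be not suspected. That default rests on the nature of the event. The one in 10.1.3 rests only on elapsed time.
3. 10.1.4 asks for an assessment of the possible relationship of pregnancy outcomes to treatment, with reporting up to one year after the estimated delivery date. Elsewhere, then, the protocol does not treat return to baseline as settling causality.
4. 4.1 promises monitoring of later effects. Continued collection under 10.1.3 honors that, so this is not a contradiction. It does show that late effects were thought possible.

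**Length of the window**

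Inputs:
- Last dose at Week 51 (protocol summary, study treatment).
- End of study at Week 72 (Section 3, Table 8-1).
- Scheduled day = 7 × week + 1. This matches Table 8-1: Week 52 = Day 365, Week 56 = Day 393, Week 68 = Day 477.
- Redacted interval taken as 98 days. This is an assumption. It is the SAP 4.1.1 on-treatment window after last dose, and it equals the 14-week contraception period in exclusion criterion 22 (14 × 7 = 98).

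Completers:
- Last dose: 7 × 51 + 1 = Day 358.
- Interval ends: 358 + 98 = Day 456.
- End of study: 7 × 72 + 1 = Day 505.
- Window: Days 457 to 505 = 505 − 456 = 49 days = 7 weeks, out of (505 − 358) / 7 = 21 weeks after last dose. It contains the Week 68 and Week 72 visits.
- If follow-up is counted as 20 weeks after last dose, as Section 3 describes it: 140 − 98 = 42 days = 6 weeks.

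Illustrative early stopper, last dose at Week 12 (Day 85), who stays to Week 72:
- Interval ends: 85 + 98 = Day 183.
- Window: Days 184 to 505 = 505 − 183 = 322 days = 46 weeks.

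**Effect on the SAP tables**

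SAP 4.1.1 ends the on-treatment period 98 days after last dose. SAP 7.1 limits safety summaries to that period (plus baseline data) and flags later data in listings. On the same 98-day assumption, an event starting in the window is outside every AE summary table however its causality is coded. It appears only in the flagged listings.

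**The case against.** The strongest case on the other side is that the safeguards stand. Every SAE reaches the sponsor, the SUSAR rule exempts no late event, 10.1.1 still asks for a relationship, the sponsor and Lead Investigator review causality jointly, and Section 10.2.4 provides an independent DMC. The clause is passive, names no one, and leaves room for attribution. It also has a stated basis: Section 8.3.4 says that the drug is cleared and immune responses have normalized after a set interval, and Section 4.5 describes the effect as reversible. Investigators are blinded, so any default applies to both arms and would not by itself distort the comparison between them.

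Most of this stands, and it rules out two stronger readings.

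- A reader might infer that late events are coded unrelated and miss SUSAR reporting. No section says either. Both are possible consequences of the default.
- A reader might infer that the related-AE tables are biased in favor of the drug. On the 98-day assumption they are not, because the SAP leaves these events out of the tables regardless of causality.

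The lymphoproliferative example should be kept in proportion too. Section 4.5 calls the risk hypothetical and ties it to strong immunosuppression, and these subjects receive no concomitant immunosuppressive therapy. Section 10.1.2 treats any malignancy as serious, so a late case would still be reported within 24 hours.

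The objection does not remove the influence of the wording on the suspicion judgement itself. The safeguards bring the case to the sponsor, but the clause says in advance how it will generally be read.

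**Conclusion.** The concern holds in a limited form. Section 10.1.3 presumes, from elapsed time alone, that late events are not due to CFZ533, and this is in tension with 10.1.1. In a first pediatric study it may push causality coding of late-appearing harms towards not suspected and so may reduce SUSAR identification. Because late events reach the study report only through flagged listings (on the 98-day assumption), the recorded relationship is one of the few signals left on them.

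The size is known only as time, and rests on that assumption about a redacted interval: 6 to 7 weeks in completers, and up to 46 weeks in the illustrative early stopper. These figures measure the window, not the bias. The documents give no basis for a count of events or of missed reports. The redaction itself is not a fault in the plan.

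**What to change.** In Protocol 10.1.3, delete the quoted non-attribution clause, from its opening conjunction to the end of the sentence, and keep the statement that AEs and SAEs continue to be collected. Add that the relationship of every AE and SAE to study treatment is assessed case by case through the last study visit, and that time since last dose is one consideration and does not decide the matter. Bring any CRF completion guidance into line.

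The cost is one sentence in the protocol and its counterpart in the guidance. No dose, visit, endpoint or analysis changes. The downside is that a few more late events may be coded as suspected. The edit does not bring late events into the SAP summary tables, since the SAP's 98-day cut-off is a separate matter.
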